### 11.2.2 Calculation of exposure adjusted incidence and event rates

The EAIR is defined as the number of subjects (n) with a specific TEAE adjusted for the exposure and will be scaled to 100 subject years:

$$EAIR = 100 \times \frac{n}{\sum_{i=1}^N TExp,i} \quad [17]$$

In the above equation, N is the total number of subjects at risk (in each PS0018 dose group) and TExp,i is the time at risk for subject i, expressed in years. Subject time at risk represents the time a subject was at risk for having a TEAE calculated as follows:

- For subjects experiencing the specific TEAE the time at risk (TExp,i) is calculated from the time of the first PS0018 dose to the onset of the TEAE. If a subject has multiple events, the time at risk is calculated relative to the first occurrence of the TEAE being considered.
- For subjects who do not experience the specific TEAE the total time at risk (TExp,i) is calculated as described in [Section 11.1.2](#).

Exact Poisson 95% CIs (lower confidence limit [LCL], upper confidence limit [UCL]) for the EAIR will be calculated using the relationship between the Poisson and the chi-square distribution (Ulm, 1990; Fay and Feuer, 1997):

$$LCL = \frac{\chi_{2n, \frac{\alpha}{2}}^2}{2}, UCL = \frac{\chi_{2(n+1), 1 - \frac{\alpha}{2}}^2}{2} \quad [18]$$

where n is the number of subjects with the specific TEAE for the incidence rate of interest and is the basis for the number of the degrees of freedom for the chi-square quantile. The LCL and UCL calculated above will be scaled to the number of subject years by dividing these by the total exposure at risk for each treatment group ( $\sum_{i=1}^N \text{TExp}, i$ ).

The EAER is defined as the total number of TEAEs (including repeat occurrences in individual subjects) divided by the total time at risk scaled to 100 subject years:

$$EAER = 100 \times \frac{n_{AE}}{\sum_{i=1}^N \text{TRisk}, i} \quad [19]$$

where  $n_{AE}$  is the total number of TEAEs and  $\text{TRisk}, i$  is the time at risk for subject i, expressed in years (calculated as described in [Section 11.1.2](#)).

No CIs will be computed for EAER.

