### 11.1 Extent of exposure

#### 11.1.1 Drug administration

All drug administration details (including date, time of injection, location, side of body and volume delivered) will be listed by subject and visit. The study medication will be given as 1 or 2 sc injections depending on dose, at each planned dosing visit (PS0018 Week 0, Weeks 4, 8, 12, 16, 20, 24, 28, 32, 40 and Week 44).

The duration of exposure (in days) will be calculated as:

$$\text{Date of last dose in PS0018} - \text{Date of first dose in PS0018} + 28 \quad [10]$$

Should the date of the last dose plus 28 days equate to a date that is beyond the Week 48 visit date then the exposure will be calculated as:

$$\text{Week 48 visit date} - \text{Date of first dose in PS0018} + 1 \quad [11]$$

For subjects who have died the exposure will be as follows:

$$\text{Date of death} - \text{Date of first dose in PS0018} + 1 \quad [12]$$

For subjects who switched dose during PS0018, the duration of dose within each dose interval (except the last dose interval) will be calculated as:

$$\text{Date of last dose in PS0018} - \text{Date of first dose in PS0018} + 1 \quad [13]$$

The dose taken in the last dose interval will be calculated as:

$$\text{Date of last dose in PS0018} - \text{Date of first dose in PS0018} + 28 \quad [14]$$

In this case duration of exposure will be calculated as the sum of the dose intervals for bimekizumab 160mg Q4W and 320mg Q4W, respectively.

Extent of exposure in PS0018 will be summarized using descriptive statistics and presented by bimekizumab 160mg Q4W, 320mg Q4W, respectively and All bimekizumab.

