#### 11.1.2 Subject time at risk

The subject time at risk represents the time a subject was at risk for having an AE and will be used to calculate the exposure adjusted incidence rate (EAIR) and exposure adjusted event rate (EAER) as described in [Section 11.2.2](#).

The subject time at risk (days) will be calculated as follows:

$$\text{Time at risk} = (\text{Date of Last PS0018 IMP} - \text{Date of First PS0018 IMP}) + 140 \quad [15]$$

This includes the duration of the SFU Period.

For subjects who switch dose during PS0018, time at risk will be derived in each dose interval and calculated as per equation [13] above, and equation [15] will be applied for the dose in the final dose interval.

In cases where the last clinical contact or last visit occurs prior to completion of the SFU period, the subject time at risk is calculated as follows:

$$\text{Time at Risk} = (\text{Date of Last Contact} - \text{Date of First PS0018 IMP}) + 1 \quad [16]$$

This will apply for the following:

- For subjects that discontinue prematurely (ie, and no SFU data are available), the date of final contact refers to the date of the latest contact with the subject during the study PS0018 after which no further information or data are available. This will be reported on the study termination page of the electronic Case Report Form (eCRF).
- For subjects that have died during the study the date of last contact refers to the date of death

The sum of these exposure days at risk across subjects in the relevant PS0018 dose group is converted to years for the EAIR and EAER calculations described in [Section 11.2.2](#).

Subject-years at risk is defined as the subject time (in days) at risk divided by 365.25. The days at risk and subject years at risk will be listed and summed by PS0018 dose at onset, together with the drug administration information ([Section 11.1.1](#)).

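### For subjects who switch dose, the dose-specific TEAE rates use wrong denominators: cases on 320 mg are timed from study start, and equation [13] drops about 27 days at each switch

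*SAP*

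**What the plan says.** SAP 11.2.1 assigns each TEAE to the PS0018 dose the subject was on at onset. SAP 11.2.3 presents EAIR and EAER by that dose, in the Any TEAE rows only.

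The EAIR denominator in SAP 11.2.2 is a sum in which "N is the total number of subjects at risk (in each PS0018 dose group"). For a subject with the event, time at risk "is calculated from the time of the first PS0018 dose to the onset of the TEAE"; with several events, "the time at risk is calculated relative to the first occurrence of the TEAE being considered". The reference to SAP 11.1.2 is made for the other subjects: "For subjects who do not experience the specific TEAE the total time at risk" comes from that section. So does the time used in the EAER.

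SAP 11.1.2 says that its time at risk "will be used to calculate the exposure adjusted incidence rate (EAIR) and exposure adjusted event rate (EAER"). It then says: "For subjects who switch dose during PS0018, time at risk will be derived in each dose interval and calculated as per equation [13] above", with equation [15] for the final interval. It adds: "The sum of these exposure days at risk across subjects in the relevant PS0018 dose group is converted to years".

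Equation [13] is in SAP 11.1.1, where "the duration of dose within each dose interval (except the last dose interval) will be calculated as" last dose date minus first dose date plus 1.

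Protocol 14.2.1 counts time up to first occurrence and presents TEAEs by treatment group, but gives no rule for dividing a switcher's time between doses. SAP 3.9 does not mention the point.

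**The concern.** A dose-specific rate needs a denominator made up of time in which an event would have been counted under that dose. Two rules break this for switchers.

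1. **Case timing (EAIR only).** A case on 320 mg carries its earlier 160 mg days into the 320 mg column. None of those days could have produced an event counted there, and a non-case does not carry them. In the same way, a first event after return to 160 mg carries 320 mg days into the 160 mg column. If a subject already had a TEAE on 160 mg, it is unclear how that subject is timed in the 320 mg column.
2. **Lost time (EAIR non-cases, EAER and exposure).** Under equation [13] a non-final interval stops on the day of its last injection. The days until the next injection fall in no interval, yet a TEAE on those days is counted under the old dose.

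Exposure-adjusted TEAE incidence is the primary safety variable, and the safety of increasing the dose to 320 mg is a secondary objective. The dose-adjustment tables in SAP 11.2.3 specify no exposure-adjusted rates, so the dose-at-onset columns are the only exposure-adjusted view of 320 mg beside 160 mg.

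**Working it through.** **Inputs from the documents.** Nominal doses on days 0, 28, ..., 308 (Week 0 to Week 44, SAP 7); 140 days added after the last dose (SAP 11.1.2); earliest increase at Week 12, day 84 (SAP 2.3); 24 to 32 days between doses (protocol 7.2); up to 45 subjects (SAP 2.4). The number of switchers, the share p with an event and the days t from switch to onset are not given, so they are assumed below.

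**The plan's own figure.** A completer who never switches has (308 − 0) + 140 = 448 days = 64 weeks. This agrees with the maximum duration in SAP 3.2.1.2.

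**Equation [13], read per interval.** For a Week 12 switch the last 160 mg injection is on day 56.
- 160 mg time: 56 − 0 + 1 = 57 days, against 84 elapsed. The loss is 27 days, or 23 to 31 days for gaps of 24 to 32 days.
- Time at risk: 57 + (308 − 84 + 140) = 57 + 364 = 421, against 448.
- Exposure: 57 + (308 − 84 + 28) = 57 + 252 = 309, against 336.
- Up at Week 12 and back at Week 24: 57 + 57 + 280 = 394, against 84 + 84 + 280 = 448.
- Effect on the 160 mg EAER, 45 subjects: with 5 switchers, (40×448 + 5×84)/(40×448 + 5×57) = 18340/18205 = 1.007; with 15 switchers, 14700/14295 = 1.028.
- Effect on the 320 mg EAER, 10 switchers, of whom some return after three 320 mg injections: 2 returning, 3080/3026 = 1.018; 5 returning, 2240/2105 = 1.064; none returning, no effect.

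**Case timing.** For switch day s, a non-case has nc = 308 − s + 140 days on 320 mg (364 for s = 84, 280 for s = 168). With no earlier TEAE on 160 mg,

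understatement of the 320 mg EAIR = 1 − [p·t + (1 − p)·nc] / [p·(t + s) + (1 − p)·nc].

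| p | t (days) | Week 12 switch | Week 24 switch |
|---|---|---|---|
| 0.1 | 120 | 2.4% | 6.0% |
| 0.2 | 30 | 5.4% | 12.7% |
| 0.4 | 120 | 11.2% | 23.7% |
| 0.8 | 30 | 41.0% | 62.7% |

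For example, p = 0.4, t = 120, s = 84: 1 − (48 + 218.4)/(81.6 + 218.4) = 1 − 266.4/300 = 11.2%.

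A sparse special-monitoring table, 1 case in 10 switchers with onset at 60 days: 1 − (60 + 9×364)/(144 + 9×364) = 2.5% for Week 12, and 6.1% for Week 24.

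**Earlier TEAE on 160 mg.** Take 10 Week 12 switchers, 7 with a first 320 mg onset 28 days after the switch. The rate per 100 subject-years is 100×7×365.25/(7d + 3×364), where d is the time counted per case:
- 320 mg time only, d = 28: 198.5.
- Study start to the 320 mg onset, d = 112: 136.3.
- Study start to an earlier 160 mg TEAE on day 20 to 60: 207.5 to 169.1.

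**Return to 160 mg.** On 320 mg from day 84 to day 168, first onset 30 days after going back: the rule counts 168 + 30 = 198 days in the 160 mg column. Actual 160 mg time is 84 + 30 = 114.

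**Precision.** The exact 95% Poisson limits are 0.27 and 2.56 times the estimate with 4 cases, and 0.43 and 1.97 times with 8.

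**The case against.** The strongest objection is that the criticism mixes two readings. It takes the first PS0018 dose in 11.2.2 literally as study start, but reads equations [13] and [15] per dose interval although their terms also refer to the first dose in PS0018. If everything is read per interval, the case-timing fault disappears. SAP 11.1.2 also makes dose-specific time the probable intent, since it names the EAIR and sums time within the dose group.

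This does not rescue the text. SAP 11.1.2 says explicitly that its time is derived per dose interval; the case rule in 11.2.2 does not, and it refers to 11.1.2 only for non-cases. Elsewhere (SAP 9 and 11.2.1) the first PS0018 dose means study start. A fully per-interval reading still leaves the 27-day gap. A fully literal reading is worse: a single switcher would get 309 days from [13] plus 448 from [15], 757 in all, for 448 days at risk.

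Several limits do stand. The phrase about the first occurrence of the TEAE under consideration could be taken as first at that dose, so the handling of an earlier 160 mg TEAE is ambiguous. Such an event is plausible after at least 12 weeks on 160 mg, so the 11% to 63% range is not a forecast. The equation [13] effect on pooled rates is small. Reporting is descriptive, the 320 mg group is selected by response, and subject and event counts are unaffected.

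**Conclusion.** The concern holds: both rules, as written, give wrong dose-specific denominators for switchers. Without an earlier 160 mg TEAE, the 320 mg EAIR is understated by 11% to 41% (Week 12 switch) or 24% to 63% (Week 24 switch) when 40% to 80% of switchers have an event, and by 2.4% to 5.4% or 6.0% to 12.7% when 10% to 20% do. With an earlier 160 mg TEAE the error can go either way. These sizes rest on assumed event shares and onset times. They lie within wide confidence intervals, but the error is systematic and avoidable. For single up-switchers without an earlier TEAE, both faults flatter 320 mg relative to 160 mg.

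Correct as written are rates for non-switchers, the All BKZ timing of cases, a single switcher's 320 mg EAER and non-case time, and the timing of a first TEAE during initial 160 mg treatment. The SAP does not say whether All BKZ time for the other subjects and for the EAER is unsplit or a sum of intervals. If summed, the All BKZ EAER rises by 0.7% to 2.1% with 5 to 15 switchers (20160/20025 and 20160/19755).

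**What to change.** Amend SAP 11.1.1, 11.1.2 and 11.2.2 as follows.

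- **Non-final intervals:** length = first injection of the next interval minus first injection of this one, for exposure and for time at risk.
- **Final interval:** dated from its own first injection. For exposure use [14], subject to the Week 48 cap [11] and the death rule [12]; for time at risk use [15] or [16].
- **EAIR by dose:** cumulative time at that dose, stopped for a case at the first onset attributed to that dose.
- **Earlier TEAE on the other dose:** state the rule, either a separate clock at each dose or removal at the first TEAE.
- **All BKZ:** use the unsplit [15]/[16], and check that the dose-specific times at risk, before stopping at events, sum to it.

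The repair closes in each case tried for a Week 12 switch. Time at risk is 84 + 364 = 448; with a return at Week 24, 84 + 84 + 280 = 448; exposure is 84 + 252 = 336. With the Week 48 visit on day 334, exposure is 84 + 251 = 335; with death on day 200, 84 + 117 = 201; with last contact on day 400, time at risk is 84 + 317 = 401. Each equals the unsplit value.

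One editorial point: the limits in [18] should be multiplied by 100, as the EAIR in [17] is. With 30 cases over 35 subject-years, [17] gives 85.7 while [18] followed by the stated division gives 0.58 to 1.22; times 100, the limits are 57.8 to 122.4.

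The cost is a few lines in a SAP amendment before database lock, which SAP section 1 requires when definitions change, and a small change to derivation code. No new data are needed.

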## 11.2 Adverse events

### 11.2.1 Definitions and classification of adverse events

All AEs will be recorded in the CRF from informed consent until study completion or termination.

Adverse events will be coded according to MedDRA® version 19.0. Treatment-emergent adverse events (TEAEs) will be defined as events that have a start date on or after the first administration of study treatment in PS0018 until the last received dose of study medication +140 days (which covers the 20-week SFU Period). Adverse events occurring after this date will not be classified as TEAEs and will therefore be excluded from the summary tables. TEAEs will be categorized according to the PS0018 dose at onset, ie, the last dose being received at the time of onset of the event. If a TEAE occurs on the same day as a change in dosage and it cannot be clearly established whether or not the TEAE started before or after dosing, because for example the time of the AE is missing, then the TEAE will be attributed to the treatment dose that the subject has just completed, unless the adverse event is related to the injection (ie higher level term (HLT) of “injection site reactions”) or an anaphylactic reaction ([Section 14.3.7.1](#)), in which case the TEAE will be assigned to the treatment dose administered on that day. Tables will include columns for BKZ 160mg Q4W, BKZ 320mg Q4W, and All BKZ.

Any adverse events considered ongoing from PS0016 which do not worsen in severity during PS0018, or starting prior to first PS0018 dose will not be considered treatment emergent in PS0018 and will be tabulated separately.

In order to evaluate if there is any difference in the TEAE profile of subjects who have dose adjustments, additional summaries will be generated based on Dose adjustment described in [Section 3.6](#) for select tables as given in [Section 11.2.3](#).

Where dates are missing or partially missing, AEs will be assumed to be treatment-emergent, unless there is clear evidence to suggest that the AE started prior to PS0018 dosing. Handling of missing dates/times for classification of AEs as TEAEs is described in [Section 4.2.4](#).

All AEs will be coded and categorized by intensity (mild/moderate/severe) and relationship to study medication (related/not related).

In summaries including relationship to study medication, the following relationship categories will be included:

- Related
- Not related

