### 11.2.3 Presentation of adverse events

An overview of the number and percentage of subjects who experience TEAEs will be presented based on the SS. This tabulation will include the number and percentage of subjects with any TEAEs, serious TEAEs, related TEAEs, discontinuation due to TEAEs, severe TEAEs, AEs leading to death and TEAEs leading to death; event counts will also be included.

- The tabulation will be presented by PS0018 dose at onset.
- This tabulation will be repeated by Dose adjustment and PS0016 randomized treatment group.

In addition, the following summaries will be presented by PS0018 dose at onset, SOC, high level term (HLT) and PT, based on the SS:

- Incidence of TEAEs by PS0018 dose at onset, including the EAIR and EAER calculated as described in [Section 11.2.2](#) for the 'Any TEAE' category only
- Incidence of TEAEs by PS0018 dose at onset, including the EAIR and EAER calculated as described in [Section 11.2.2](#) for the 'Any TEAE' category only by overall ADA status (positive/negative)
- Incidence of TEAEs by Dose adjustment and PS0016 randomized treatment group
- Incidence of serious TEAEs by PS0018 dose at onset and Dose adjustment
- Incidence of TEAEs by relationship and PS0018 dose at onset
- Incidence of TEAEs by maximum relationship and PS0018 dose at onset
- Incidence of TEAEs by maximum intensity and PS0018 dose at onset
- Incidence of fatal TEAEs by relationship and PS0018 dose at onset

- Incidence of serious TEAEs by relationship and PS0018 dose at onset
- Incidence of non-serious TEAEs above threshold of 5% of subjects by PS0018 dose at onset
- Incidence of non-serious TEAEs above threshold of 5% of subjects by relationship and PS0018 dose at onset
- Incidence of ongoing AEs from PS0016
- Incidence of ongoing AEs from PS0016 which do not worsen in severity, or AEs started prior to PS0018 dose, by PS0016 randomized treatment group

In addition, separate AE summaries by PS0018 dose at onset, SOC, HLT and PT will be included for the following AEs of special monitoring (AESM) further defined in [Section 14.3](#).

- Major cardiovascular events
- Serious infections, including opportunistic infections and tuberculosis (TB)
- Malignancies including lymphoma
- Cytopenias
- Neuropsychiatric events (in particular, depression and suicide)
- Inflammatory bowel disease
- Anaphylactic reaction (hypersensitivity and anaphylactic reactions)
- Hepatic events and drug-induced liver injury

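### SAP 11.2.2 leaves the EAIR confidence limits 100 times too small, and SAP 11.1.2 and 11.2.2 do not give one workable definition of a dose switcher's time at risk

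*SAP*

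**What the plan says.** SAP 11.2.2, equation [17], defines the EAIR as the number of subjects with the TEAE "adjusted for the exposure and will be scaled to 100 subject years", with each subject's time at risk in years. Equation [18] gives exact Poisson limits for the count. The only scaling of those limits is this: "The LCL and UCL calculated above will be scaled to the number of subject years by dividing these by the total exposure at risk". Protocol 14.2.1 divides the summed subject-years by 100 and presents the confidence interval with that rate.

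For a subject with the event, SAP 11.2.2 says the time at risk "is calculated from the time of the first PS0018 dose to the onset of the TEAE". Only subjects without the event are sent back to 11.1.2. Section 11.1.2 says its time at risk serves both the EAIR and the event rate (EAER). For subjects who change dose, "time at risk will be derived in each dose interval and calculated as per equation [13] above", with equation [15] for the final interval. It adds: "The sum of these exposure days at risk across subjects in the relevant PS0018 dose group is converted to years".

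Equation [13] comes from SAP 11.1.1, where "the duration of dose within each dose interval (except the last dose interval) will be calculated as" the last dose in PS0018 minus the first dose in PS0018, plus 1. Equations [15] and [16] also start at the first PS0018 dose. Under SAP 11.2.1 each TEAE goes to the dose at onset, meaning "the last dose being received at the time of onset of the event".

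**The concern.** The EAIR interval is the only confidence interval specified for the primary safety variable, since the EAER has none. Programmed as written, it would be on a different scale from the estimate beside it.

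The second problem affects the dose columns. All subjects start on 160mg, and some may move to 320mg from Week 12. If a 320mg event is divided by time running from the first PS0018 dose, 160mg time enters the 320mg denominator. The safety of increasing the dose is a stated secondary objective, so the 320mg column matters.

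The third is that the equations for splitting time between doses are written with whole-study dates. Applied to intervals, they do not add up to the time the subject was at risk.

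**Working it through.** The documents print no EAIR or interval, so there is no figure to reproduce. Inputs from the documents are: up to 45 subjects (SAP 2.4), last dose at Week 44 (SAP 3.2.1.2), 140 days after the last dose (SAP 11.1.2), 365.25 days per year (SAP 11.1.2), and dosing every 4 weeks. Event counts, event rates, switch weeks and the 20 subject-years used below are assumptions.

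**1. Scale of the limits.** On the count scale, LCL = chi-square(2n, 0.025)/2 and UCL = chi-square(2(n+1), 0.975)/2. For n = 30 these are 20.24 and 42.83.

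- Assumed 20 subject-years: EAIR = 100 × 30/20 = 150.
- Limits as written: 20.24/20 = 1.01 and 42.83/20 = 2.14.
- Limits times 100: 101.2 and 214.1.

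A second case uses the largest exposure the plan allows without stopping at events: 45 × 448/365.25 = 55.20 subject-years. With n = 10 the EAIR is 18.12; the written limits are 0.087 to 0.333, and times 100 they are 8.69 to 33.32.

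This does not depend on the example. The written UCL divided by the EAIR equals (count-scale UCL)/(100n). The count-scale UCL is largest relative to n at n = 1, where it is 5.57. So for n from 1 to 45 the written UCL is at most 5.57/100 = 5.6% of the estimate.

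**2. Time origin in the 320mg column.** Take a single switch at week w and a constant true rate r per year. Let S = 7w days on 160mg and T = (44 − w) × 7 + 140 days at risk on 320mg, both converted to years. Let p = 1 − exp(−rT), q = 1 − exp(−rS), and E(X) = mean event time given an event before X.

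- Time on 320mg only: p / [p E(T) + (1 − p)T] = r, which is unbiased.
- 11.2.2, with first occurrence meaning first on 320mg (reading A): p / [p(S + E(T)) + (1 − p)T].
- 11.2.2, with first occurrence meaning first in PS0018 (reading B): p / [p(q E(S) + (1 − q)(S + E(T))) + (1 − p)T].

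Worked case, reading A, w = 12, r = 1 (100 per 100 subject-years): S = 84 days = 0.2300, T = 364 days = 0.9966, p = 0.6309, E(T) = 0.4169. The rate is 0.6309 / [0.6309 × 0.6469 + 0.3691 × 0.9966] = 0.6309/0.7760 = 0.813, or 81.3 per 100.

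| Switch week | True 100, A | True 100, B | True 20, A | True 20, B |
|---|---|---|---|---|
| 12 | 81.3 | 89.3 | 19.1 | 19.2 |
| 24 | 68.5 | 80.3 | 18.3 | 18.5 |
| 32 | 62.0 | 75.1 | 17.8 | 18.0 |

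Nonadjusters are unaffected. So is the All BKZ column, where the first PS0018 dose is the right origin.

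**3. Interval equations.** Take a switch at Week 12: 160mg doses on days 0, 28 and 56, and 320mg doses from day 84 to day 308. Time at risk by equation [15] over the whole study is 308 + 140 = 448 days.

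- Read literally, with first and last dose in PS0018: [13] gives 308 + 1 = 309 and [15] gives 448. The sum is 757, so time is double-counted.
- Read per interval: [13] gives 56 + 1 = 57 and [15] gives (308 − 84) + 140 = 364. The sum is 421, and 448 − 421 = 27 days count nowhere. Under 11.2.1 a TEAE in that gap still goes to 160mg.

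**The case against.** The missing factor is an evident drafting slip. Equation [17] and Protocol 14.2.1 both show that per 100 is meant, and an interval that excludes its own estimate would be conspicuous in a table. That is fair as to likelihood, but no SAP text supplies the factor, and the SAP is what gets programmed.

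On time at risk, a reader might infer that the plan makes 320mg look safer. The documents do not support that as a fact. Section 11.1.2 has a specific rule for switchers, says it feeds the EAIR, and sums time by dose group. If that rule governs, no 160mg time is carried over. The downward bias therefore depends on following 11.2.2, and its size on assumed rates and switch weeks. The dose columns are also descriptive, and 320mg is reached by non-randomised selection on response.

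A reader might likewise say that the interval rule simply loses time. That holds only on the per-interval reading; the printed wording double-counts. The defect is that neither reading gives 448 days.

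A reader might also object that the rates appear "for the 'Any TEAE' category only", whereas the protocol places them in the summary by SOC, HLT and PT. I do not press this. The protocol asks that the summary include the rates, and the SAP does include them. At most the restriction should be declared in SAP 3.9.

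**Conclusion.** The confidence limits are wrong as written, by exactly 100 relative to the estimate, whatever the exposure. This rests on no assumption beyond the text, and correcting it leaves equation [18] itself intact.

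The conflict between 11.1.2 and 11.2.2 is real and should be resolved before programming. If 11.2.2 prevails, the 320mg EAIR would be biased low, materially at high rates and slightly at low ones. The figures illustrate this under constant rates and one switch; the documents give no expected rates or switch weeks.

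The interval equations need restating on either reading. This should be fixed, but it does not undermine the design or the data collected.

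**What to change.** **11.2.2, limits.** Write LCL = 100 × chi-square(2n, α/2) / (2 × total exposure in years) and UCL = 100 × chi-square(2(n+1), 1 − α/2) / (2 × total exposure in years).

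**11.1.2, interval dates.** Define these once. Each interval starts at the first dose at that level. Each non-final interval ends at the first dose of the next level. The final interval runs from its own first dose to the last dose + 140 days, or to last contact or death where equation [16] applies. Restate equations [13], [15] and [16] on those dates for time at risk. Changing [13] alone is not enough: with [15] still starting at the first PS0018 dose, the Week 12 switcher would get 84 + 448 = 532 days. With all three restated the sum is 84 + 364 = 448.

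**11.2.2, time origin.** In each dose column count only time on that dose, up to the first onset on that dose. For All BKZ keep the first PS0018 dose as the origin and the first occurrence in PS0018 as the end.

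The cost is SAP wording and one by-dose time-at-risk derivation, with no new data.
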